Active treatment period: The planned duration of treatment is until disease progression. Subjects may be discontinued from treatment earlier due to unacceptable toxicity or other discontinuation criteria are met. End of Treatment (EOT) evaluations will be performed at the time of decision to discontinue treatment (or as close to the decision day as possible). Subjects may continue to receive up to a maximum of 24 months of nivolumab. Subjects who are still deriving clinical benefit after 24 months may continue to receive ivosidenib monotherapy until disease progression, unacceptable toxicity, or other discontinuation criteria are met.

Safety Follow-up period: Following discontinuation from study treatment, all subjects will have a 30-day Safety Follow-up visit. During the 30 (+5)-day Safety Follow-up period, all AEs and new medications (including new anti-cancer therapy) will be reported. Following the 30 (+5)-day Safety Follow-up period, subjects will be followed for safety for an additional 100 (+5) days after their last dose of immunotherapy or until they begin any other anti-cancer therapy, whichever is earlier.

Overall Survival (OS) Follow-up period: Subjects will be followed for OS. Subjects will be contacted every 12 weeks (\pm 2 weeks) beginning at the EOT visit for up to 2 years after the last subject has been enrolled, or until death, lost to follow-up, withdrawal of consent from overall study participation, or Sponsor ending study, whichever occurs first.

Data Review Team: A DRT composed of Sponsor medical, safety, and statistical representatives and study Investigator(s) will review the available safety data in all subjects enrolled in the 500 mg QD dose cohort of the Safety Lead-in phase in order to determine whether 500 mg QD is the ivosidenib RCD or whether the 250 mg QD dose level will be tested. If the 250 mg QD dose cohort is opened, the DRT will review the safety data in order to determine whether 250 mg QD is the RCD for the Expansion phase.

Contractual signatories

I, the undersigned, have read the foregoing protocol and the “Participant information and consent form” document attached to the protocol and agree to conduct the study in compliance with such documents, Good Clinical Practice and the applicable regulatory requirements.

INVESTIGATOR

NAME	
CENTER NUMBER	
DATE	
SIGNATURE	

**VICE PRESIDENT, CLINICAL DEVELOPMENT
HEAD OF CANCER METABOLISM GLOBAL DEVELOPMENT**

NAME	PPD
DATE	06 May 2024
SIGNATURE	PPD

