4.1.1.5. Post-Withdrawal Follow-up and End of Study

Safety Follow-up: Following discontinuation of study treatment, a post-treatment Safety Follow-up visit is to occur 30 (+5) days after the last dose of ivosidenib and immunotherapy. Subjects will be followed for an additional 100 (+5) days after the last dose of immunotherapy, unless they have started another anti-cancer therapy, whichever occurs earlier. Every effort must be made to perform protocol-specified evaluations unless consent to participate in the study is withdrawn.

PFS and Overall Survival Follow-up: Subjects who discontinue study treatment for reasons other than disease progression or withdrawal of consent from treatment and are alive by EOT will enter PFS follow-up with the same schedule of assessments as before study treatment discontinuation, until documented disease progression, death, the start of subsequent anti-cancer therapy, withdrawal of consent, or the end of study/study termination. Following discontinuation of study treatment, all subjects will be followed for survival. Subjects will be contacted every 12 weeks (\pm 2 weeks) after the subject experiences documented disease progression or begins subsequent anti-cancer therapy. This contact will continue for up to 2 years after the last subject has been enrolled, or until end of study, withdrawn consent, or are lost to follow-up, or the Sponsor has terminated the study, whichever occurs first.

Each subject will have an End of Study visit defined as the time at which the subject has permanently discontinued treatment and has completed the Safety Follow-up visit and survival follow-up period, or has died, been lost to follow-up, or withdrawn consent from the study or the Sponsor has terminated the study, whichever occurs first.

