16. If a subject goes off treatment for reasons other than disease progression or withdrawal of consent from treatment, response assessments will be conducted at the EOT visit.
17. Ivosidenib is to be taken daily. Subjects should be instructed to take their daily dose at approximately the same time each day. Each daily dose should be taken with or without food. Subjects taking ivosidenib with food should be advised to avoid grapefruit or grapefruit products and avoid consuming a high-fat meal. If the subject forgets to take the daily dose, then they should take ivosidenib within 12 hours after the missed dose. If more than 12 hours have elapsed, then that dose should be omitted, and the subject should resume treatment with the next scheduled dose. The dose on C1D1, C1D15, and Day 1 of each cycle thereafter is to occur in-clinic to allow for pre-treatment assessments and to accommodate PK sampling. In subjects receiving the combination, on days when nivolumab and ipilimumab are administered, ivosidenib should be administered approximately 30 minutes before the start of the nivolumab infusion.
18. Nivolumab is to be administered over an approximately 30-minute IV infusion. Sites should make every effort to target infusion timing to be as close to 30 minutes as possible. However, given the variability of infusion pumps from site to site, a window between -5 minutes and +10 minutes is permitted (*i.e.*, infusion time is 30 minutes (-5 minutes/+10 minutes). When study treatments nivolumab and ipilimumab are to be administered on the same day, nivolumab is to be administered first. Nivolumab infusion must be promptly followed by a flush of diluent to clear the line of nivolumab before starting the ipilimumab infusion. The second infusion will always be the ipilimumab study treatment and will start after the infusion line has been flushed, filters changed, and subject has been observed to ensure that no infusion reaction has occurred.

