5.4. Participant Withdrawal

5.4.1. Withdrawal Criteria

Premature discontinuation of IMP does not mean that the subject prematurely stops the participation in the study.

Subjects discontinuing study treatment for reasons other than withdrawal of consent from overall study participation will be expected to continue in the study including Safety Follow-up visits and be contacted for survival follow-up. Information to be collected during the last visit for these subjects is given in Section 5.4.3.

The reasons for premature discontinuation of IMP are:

- AEs, according to the judgment of the Investigator, including no recovery in safety parameters.
- Disease progression as assessed by the Investigator/site radiologist according to RECIST v1.1 ([Appendix 12](#)). Clinically stable subjects may continue beyond confirmed disease progression if benefits are expected to outweigh risks in the opinion of the Investigator and in consultation with the Sponsor.
- Clinical disease progression manifested by symptomatic deterioration.
- Completion of a maximum of 24 months of nivolumab (note that subjects receiving combination may continue to receive ivosidenib monotherapy).
- Pregnancy (for reporting, see Section [8.10.2.3](#)).
- Major protocol deviation if it interferes with the study evaluations and/or if it jeopardizes subject's safety, e.g., any medical event requiring administration of an unauthorized concomitant treatment (see Section [6.3](#)).
- Withdrawal of consent (only for IMP discontinuation): Subjects will be asked if they are willing to continue the safety and disease/survival follow-up.
- Physician decision (for reasons that cannot be included in any of the criteria listed above, for example, availability of a better therapeutic alternative for the subject).
- Study terminated by Sponsor.

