8.12. Dose Modification and Management for Adverse Events

8.12.1. Study Treatment Dose Modification and Management Associated with Ivosidenib

For any AE, including AEs not specifically mentioned in [Table \(8.12.1\) 1](#), the Investigator may decide to delay dosing or modify the dose of ivosidenib based on clinical judgment. These decisions should be discussed with the Sponsor prior to implementation. Dose modifications of ivosidenib from 500 mg to 250 mg will be permitted on study for management of AEs ([Table \(8.12.1\) 1](#)). If more than one AE occurs that would require a dose modification, upon resolution of all AEs to baseline or Grade 1, ivosidenib should be dose reduced to 250 mg. Re-escalation may be allowed with approval from the Sponsor.

Dose delays are discouraged, except as needed for management of AEs. Dose delays up to 28 days will be permitted at the discretion of the Investigator in consultation with the Sponsor for reasons including management of AEs and for mitigating circumstances (e.g., planned procedures). Palliative biliary decompression procedures will be permitted on study and will not require interruption of ivosidenib (see Section 8.12.5).

If the subject cannot resume ivosidenib within 28 days, the subject should be discontinued from ivosidenib. Other reasons for treatment termination are provided in Section 5.4.1. If ivosidenib is discontinued, the subject may continue receiving nivolumab and ipilimumab or nivolumab alone. If subject permanently discontinues treatment from all three drugs, the EOT and Safety Follow-up visits will be completed as well as the PFS follow-up (if disease has not progressed) and Survival Follow-up visits. Exemptions may be considered for those subjects who are determined by the Investigator to have received clinical benefit from treatment. If a dose is delayed for the management of an AE, the subject should resume the study at the next planned visit within a dosing cycle.

If a strong CYP3A4 inhibitor must be co-administered, reduce the ivosidenib dose to 250 mg QD. If the strong inhibitor is discontinued, increase the ivosidenib dose (after at least 5 half-lives of the strong CYP3A4 inhibitor) to the recommended dose of 500 mg QD.

Table (8.12.1) 1 - Management of Ivosidenib related QT Prolongation and Adverse Events by NCI CTCAE Grade

NCI CTCAE Grade	Management

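### Participants who withdraw consent only from treatment are left out of PFS follow-up (Protocol 4.1.1.5) and the EOT response assessment (footnote 16), although other sections keep willing participants under evaluation

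*Protocol*

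**What the plan says.** Two places exclude a participant who withdraws consent for treatment only:

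- Protocol 4.1.1.5, on who is followed for PFS: "Subjects who discontinue study treatment for reasons other than disease progression or withdrawal of consent from treatment and are alive by EOT will enter PFS".
- Table (4.1.2) 1, footnote 16, on the EOT visit and repeated in the UK table in Appendix 13: "If a subject goes off treatment for reasons other than disease progression or withdrawal of consent from treatment, response assessments will be conducted".

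Several places keep that participant under evaluation:

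- Section 5.4.1 treats this as its own category: "Withdrawal of consent (only for IMP discontinuation): Subjects will be asked if they are willing to continue the safety and disease/survival follow-up".
- Section 5.4.2 stops evaluations only when consent is withdrawn from the study as a whole, and expressly not for treatment alone.
- Section 4.1.1.4 gives every subject an EOT assessment, with withdrawal of study consent as the only exception to making every effort.
- Footnote 15 asks for a response assessment unless treatment stopped for progression or new anticancer therapy. It has no consent exception.
- Section 8.12.1 says that when all three drugs are stopped for good, "the EOT and Safety Follow-up visits will be completed as well as the PFS follow-up (if disease has not progressed) and Survival Follow-up visits". Section 8.12.2 says the same.

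Footnote 3 (main and UK tables) and SAP 1.2.1 exclude withdrawal of consent without saying which kind.

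On survival, 4.1.1.5 says all subjects are followed, but it and footnote 26 start the 12-weekly contact "after the subject experiences documented disease progression or begins subsequent anti-cancer therapy". The synopsis says: "Subjects will be contacted every 12 weeks (\pm 2 weeks) beginning at the EOT visit". SAP 1.2.1 starts survival assessments after EOT unless the participant is in PFS follow-up.

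**The concern.** Section 5.4 separates stopping treatment from leaving the study. Section 4.1.1.5 and footnote 16 then treat the first like the second where imaging is concerned. A site could ask a participant to accept continued disease follow-up under 5.4.1, obtain agreement, and find that 4.1.1.5 offers no scans.

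Two things are at stake under the protocol's design. First, a decision to stop may reflect poor tolerability or feeling worse. If progression scans end at that decision, any PFS censoring that results may be informative. Second, the protocol requires a response to be confirmed at least 4 weeks after it is first seen, so an omitted EOT scan can leave a response unconfirmed. The conflicting start of survival contact affects the same participants. Someone who has not progressed, is not being scanned and has no new therapy may not meet the 4.1.1.5 trigger for the 12-weekly calls.

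**Working it through.** The plan states no figure on this point, so the check is mainly a comparison of text.

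**1. One participant, each rule.** Take a participant who has stopped all three drugs by withdrawing consent for treatment, has not progressed, and agrees to further scans.

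| Place | Instruction |
|---|---|
| 4.1.1.5 | Does not enter PFS follow-up |
| Footnote 16 (main, UK) | No EOT response assessment |
| Footnote 15 | EOT response assessment |
| 4.1.1.4 | EOT evaluations attempted |
| 5.4.1 | Asked to continue disease follow-up; has agreed |
| 5.4.2 | Evaluations not stopped |
| 8.12.1, 8.12.2 | PFS follow-up |
| Footnote 3 (main, UK), SAP 1.2.1 | Unclear |

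The EOT radiographic cell carries footnotes 15 and 16 together, so that one cell gives two answers.

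**2. Effect on PFS.** Protocol 10.1.6.1 leaves PFS censoring to the SAP, and the SAP contains no such rule. The nearest written rule, for duration of response, censors at the last evaluable response assessment. If PFS followed it, the date would be the last scan before stopping. Deaths count as PFS events, so a later death could still be one.

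**3. Effect on confirmation.** Three inputs matter: confirmation at least 4 weeks after first response (7.2; SAP 5.3), an EOT visit within 7 days of the last dose (4.1.1.4), and a BOR window that closes at end of treatment (10.1.6.1; SAP 5.3).

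- PR at Week 6, last dose at Week 9. An EOT scan falls at Weeks 9 to 10, which is 9 − 6 = 3 to 10 − 6 = 4 weeks later. It misses the minimum or only just reaches it. The Week 12 scan is after end of treatment and outside the BOR window, whether or not PFS follow-up is open.
- PR at Week 6, last dose at Week 11, no Week 12 scan yet. An EOT scan falls at Weeks 11 to 12, which is 11 − 6 = 5 to 12 − 6 = 6 weeks later. It could confirm the PR if the EOT visit counts as inside the window. Here footnote 16 matters. Without the scan, BOR is SD, because nominal Week 6 is day 42, past the 36-day minimum in SAP 5.3.

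The loss through footnote 16 is therefore possible but depends on timing. The BOR window is a second, separate limit.

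**4. Scale, illustration only.** One response in a planned cohort of 40 is 1/40 = 2.5 percentage points. With exact 95% intervals and assumed counts:

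- 9/40 = 22.5% (10.8 to 38.5)
- 8/40 = 20.0% (9.1 to 35.6)

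Among the 7 enrolled, one participant is 1/7 = 14.3% of those listed.

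**The case against.** The strongest reply is that this is a wording mismatch with little consequence. Much of it stands.

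- **The EOT scan is not simply abolished.** Footnote 15 and section 4.1.1.4 support it, and 5.4.3 says an EOT visit should always be offered. The scan is lost only where a site lets footnote 16 prevail. That is a conflict to resolve, and nothing in the protocol says which footnote governs.
- **The supporting sections are not all emphatic.** Section 5.4.1 only asks whether the participant is willing. Sections 8.12.1 and 8.12.2 concern dose modification and do not mention consent. The unqualified wording in footnote 3 and SAP 1.2.1 could mean study withdrawal. The explicit exclusion from PFS follow-up therefore rests on 4.1.1.5.
- **A reader might infer that PFS is censored at the decision to stop.** No document says so, because no PFS censoring rule is written.
- **A reader might infer that survival follow-up never begins.** Section 4.1.1.5 says all subjects are followed for survival, and 5.4.1 expects contact. Only the start of the 12-weekly calls is in conflict.
- **A reader might infer that reopening PFS follow-up restores lost responses.** It does not while the BOR window closes at end of treatment. A participant stopping for an adverse event meets the same limit.
- **No ORR or PFS estimate is planned.** SAP 3.1 drops the objective response endpoint, and SAP 5 and 5.3 confine efficacy to listings. This limits the present effect but does not reconcile the protocol.

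**Conclusion.** The contradiction is real and worth correcting. Section 4.1.1.5 and footnote 16 exclude treatment-only withdrawers from progression follow-up and the EOT response assessment, against 4.1.1.4, 5.4.1, 5.4.2, 8.12.1, 8.12.2 and footnote 15. Under the protocol's design this risks informative PFS censoring and, at some timings, an unconfirmed response. The start of the 12-weekly survival contact is a separate inconsistency.

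The size cannot be estimated, because the documents do not give the number of treatment-only withdrawals. The 2.5-point figure describes the planned expansion cohort, which did not open. With enrollment stopped at 7, the effect now is on how the response and BOR listings are read. The conclusion assumes that a site could act on 4.1.1.5 and footnote 16 as worded, and that some withdrawers would accept scans. It does not depend on any particular PFS censoring rule.

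**What to change.** 1. In Protocol 4.1.1.5, footnotes 3 and 16 (main and UK tables) and SAP 1.2.1, limit the exclusion to withdrawal of consent from overall study participation or from disease follow-up. Treatment-only withdrawers who agree then have the EOT response assessment and PFS follow-up.
2. In 4.1.1.5 and footnote 26, start the 12-weekly survival contact at EOT for anyone not in PFS follow-up, in line with the synopsis and SAP 1.2.1.
3. In Protocol 10.1.6.1 and SAP 5.3, state whether scans after end of treatment but before new anticancer therapy can confirm a response. Appendix 4 itself asks protocols to be clear on post-treatment assessments. Without this, step 1 does not restore confirmation.
4. In the present listings, identify treatment-only withdrawers, so that a BOR of SD or NE caused by a missing scan is not misread.

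The cost is wording in a few places, a flag in the listings, and a few scans on the existing schedule for participants who agree to them.

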4.1.1.6. End of Trial

End of trial is defined as the date of the last visit/follow-up of the last subject (including visit or remote contact), or the date of the last contact attempt if the last subject is declared lost to follow-up.

4.1.2. Investigation Schedule

Assessments for subjects in the Safety Lead-in and Expansion phases are in [Table \(4.1.2\) 1](#). PK and PD blood sampling are described in [Table \(4.1.2\) 2](#) and [Table \(4.1.2\) 3](#) for the Safety Lead-in phase and Expansion phase, respectively.

Table (4.1.2) 1 - Schedule of Assessments for Subjects in the Safety Lead-in Phase and Expansion Phase

Visit/Cycle	Screening ¹	Cycle 1 (21 Days)			Cycle 2 (21 Days)		Cycles 3 and 4 (21 Days)	Cycle 5 and Beyond (28 Days Each Cycle)	End of Treatment ²	Safety Follow-up ²		PFS Follow-up ³	Survival Follow-up
Study Day	D-28 to D-1	D1	D8	D15 (± 2 Days)	D1 (± 2 Days)	D15 (± 2 Days)	D1 (± 2 Days)	D1 (± 2 Days)	Within 7 Days After Last Dose	30 (+5) Days After Last Dose	100 (+5) Days After Last Nivolumab Dose		Every 12 weeks (± 2 weeks)
Allocation to IMP ⁴		X			X		X	X					
Informed Consent	X												
Inclusion/Exclusion Criteria	X												
Demographics	X												
Disease History	X												
Medical and Surgical History	X												
Complete Physical Exam	X												
Limited Physical Exam		X		X	X	X	X	X	X				
Height and Weight ⁵	X	X			X		X	X					
ECOG Performance Status	X	X			X		X	X	X	X			
Vital Signs ⁶	X	X		X	X	X	X	X	X	X			
12-lead ECG ^{7,8}	X	X	X	X	X		X	X	X	X			
LVEF (ECHO, MUGA scan, or by other method according to institutional practice)	X												
Hematology ⁹	X	X		X	X	X	X	X	X				
Serum Chemistry ¹⁰	X	X		X	X	X	X	X	X				
Coagulation Studies ¹¹	X												
Pregnancy Test ¹²	X ¹²	X ¹²			X ¹²		X ¹²	X ¹²	X ¹²				
Thyroid Function Tests ¹³	X	X					X (only at C3D1)	X (every other cycle)	X				
Radiographic Evaluation of Disease ¹⁴	X (D-21 to D-1)						X (only C3D1) ¹⁵	X ¹⁵ (every other cycle)	X ^{15,16}			X	
Ivosidenib Administration ¹⁷						X							

Visit/Cycle	Screening ¹	Cycle 1 (21 Days)			Cycle 2 (21 Days)		Cycles 3 and 4 (21 Days)	Cycle 5 and Beyond (28 Days Each Cycle)	End of Treatment ²	Safety Follow-up ²		PFS Follow-up ³	Survival Follow-up
Study Day	D-28 to D-1	D1	D8	D15 (± 2 Days)	D1 (± 2 Days)	D15 (± 2 Days)	D1 (± 2 Days)	D1 (± 2 Days)	Within 7 Days After Last Dose	30 (+5) Days After Last Dose	100 (+5) Days After Last Nivolumab Dose		Every 12 weeks (± 2 weeks)
Nivolumab Administration ¹⁸		X			X		X	X (every cycle)					
Ipilimumab Administration ¹⁹		X			X		X						
IMP Compliance ²⁰					X		X	X	X				
Tumor Biopsy ²¹	X						X (± 7 days for biopsy collection)		X				
Buccal Swab for Germ-line Mutation Analyses ²²	X												
Blood Sampling for Exploratory Biomarkers ²³	X				X		X	X	X				
Adverse Events ²⁴	X	X		X	X	X	X	X	X	X			
Prior and Concomitant Medications/Procedures ²⁵	X	X		X	X	X	X	X	X	X			
Subsequent Anti-cancer Therapy									X	X	X	X	X
Survival Status ²⁶													X

Abbreviations: AE = adverse event; C = Cycle; CFR = Code of Federal Regulations; CT = computed tomography; D = Day; ECG = electrocardiogram; ECHO = echocardiography; ECOG = Eastern Cooperative Oncology Group; eCRF = electronic case report form; EOT = End of Treatment; FFPE = formalin-fixed paraffin-embedded; GDPR = General Data Protection Regulation; HIPAA = Health Insurance Portability and Accountability Act; ICF = informed consent form; IDH1 = Isocitrate dehydrogenase-1; IMP = investigational medicinal product; IV = intravenous; LVEF = left ventricular ejection fraction; MRI = magnetic resonance imaging; MUGA = multiple gated acquisition; PFS = progression-free survival; Q3W = once every 3 weeks; Q4W = once every 4 weeks; QTcF = heart rate-corrected QT interval by Fridericia's method; RTSM = Randomisation and Trial Supply Management; SAE = serious adverse event.

Note One, or two if required by local regulation, original information and consent form(s) must be completed, dated, and signed personally by the participant and by the person responsible for collecting the informed consent. According to each study participant's own preference, the ICF could be made available both printed on paper or/and electronically through a HIPAA, 21 CFR Part 11, and GDPR compliant web-based platform. Local regulations permitting, the electronic signature for the ICF could be made available to interested study participants. Interested study participants will be offered the possibility to replace certain in-person visits to the research site by televisits. This means that some study visits could be conducted using a HIPAA, 21 CFR Part 11, and GDPR compliant web-based platform, as per each study participant's own preference. Follow-up (for survival status until the end of the study) can be done remotely by using various telecommunication technologies including but not limited to phone, web-based remote video-calling, and shared electronic medical records.

1. Day -28 is relative to first dose of IMP.
2. All subjects will undergo an EOT assessment within 7 days after the last dose of IMP (for combination, this is to occur after all 3 IMPs have been discontinued). However, when this is not possible (e.g., dose delay more than 7 days), EOT assessment can be performed at the 30-day safety follow-up visit. A second Safety Follow-up will occur 100 (+5) days after last nivolumab dose or ipilimumab if no other anti-cancer therapy is initiated.
3. Subjects who discontinue study treatment for reasons other than disease progression or withdrawal of consent and are alive by EOT will enter PFS follow-up with the same schedule of assessments as before study treatment discontinuation, until documented disease progression, death, start of subsequent anti-cancer therapy, withdrawal of consent, or the end of study/study termination.
4. Allocation of IMP will occur via RTSM.
5. Height is to be obtained only at Screening assessment.
6. Systolic and diastolic blood pressure, heart rate, respiratory rate, and temperature. Assessments should be conducted while the subject is seated or supine.
7. Subjects with a QTcF of \geq 450 msec at baseline will not be allowed to enroll in the study. Up to three 12 lead ECG tests under stable condition can be performed at each visit during screening and throughout treatment and study follow-up.
8. ECG can be performed at any time during the study visit (on-site or at local clinic); however, it is required once weekly for the first 3 weeks of treatment, and then once every cycle for the duration of therapy.
9. Hematocrit, hemoglobin, red blood cell count, white blood cell count with differential, and platelet count. Hemoglobin criteria of \geq 9.0 g/dL or \geq 5.6 mmol/L at Screening must be met without packed red blood cell transfusion within the prior 2 weeks. Subjects can be on stable dose of erythropoietin (\geq approximately 3 months). On C1D1, assessments should be conducted prior to IMP administration.
10. Sodium, potassium, chloride, calcium, magnesium, phosphorus, carbon dioxide, albumin, glucose, blood urea nitrogen (BUN)/UREA, creatinine, alkaline phosphatase, alanine aminotransferase, aspartate aminotransferase, gamma glutamyl transferase, total bilirubin, direct bilirubin, and indirect bilirubin. On C1D1, assessments should be conducted prior to IMP administration.
11. Activated partial thromboplastin time and either prothrombin time or international normalized ratio.
12. For women of childbearing potential, a serum pregnancy test will be performed at Screening, and a urine pregnancy test will be conducted on the day of IMP administration and is to be confirmed negative prior to dosing. If the urine pregnancy test is positive and cannot be confirmed negative, a serum pregnancy test must be performed and shown to be negative within 24 hours prior to the first day of IMP administration. An extension up to 72 hours prior to the start of study treatment is permissible in situations where the results cannot be obtained within the standard 24-hour window.
13. Thyroid function test includes triiodothyronine (T3) or free T3, free thyroxine, and thyroid stimulating hormone. Thyroid function tests are to be performed every 6 weeks for the first 4 cycles and then every 8 weeks starting from Cycle 5 and to be performed at EOT. On C1D1, assessments should be conducted prior to IMP administration. Thyroid function test results obtained after the visit are acceptable so long as the value at screening was normal or considered not clinically significant per investigator assessment.
14. Tumor assessments will include all known or suspected disease sites. CT imaging of the chest, abdomen, and pelvis (torso) with triphasic IV contrast should be performed at baseline and on study. For subjects with allergy to IV iodine contrast, CT chest without IV contrast and MRI abdomen with IV contrast should be performed at baseline and on study. Brain scans with CT or MRI should be performed at baseline in subjects with known treated brain metastases and on study at the same imaging time points as torso imaging. Additional anatomy should be imaged based on the signs and symptoms of individual subjects at baseline and follow-up. Radiographic assessment (CT or MRI or other imaging modalities as appropriate per RECIST v1.1 Appendix 4) for evaluation of disease response to be conducted at Screening (Day -21 to Day -1), every 6 weeks (\pm 7 days) for the first 2 assessments (*i.e.*, through Week 12), and then every 8 weeks (\pm 7 days) thereafter independent of dose delays and/or dose interruptions, and/or at any time when progression of disease is suspected. Tumor assessment frequency can be reduced to every 12 weeks after 2 years of treatment initiation.
15. Response to treatment is to be assessed at this visit if the subject discontinues treatment for reasons other than disease progression or start of another anticancer therapy.
16. If a subject goes off treatment for reasons other than disease progression or withdrawal of consent from treatment, response assessments will be conducted at the EOT visit.
17. Ivosidenib is to be taken daily. Subjects should be instructed to take their daily dose at approximately the same time each day. Each daily dose should be taken with or without food. Subjects taking ivosidenib with food should be advised to avoid grapefruit or grapefruit products and avoid consuming a high-fat meal. If the subject forgets to take the daily dose, then they should take ivosidenib within 12 hours after the missed dose. If more than 12 hours have elapsed, then that dose should be omitted, and the subject should resume treatment with the next scheduled dose. The dose on C1D1, C1D15, and Day 1 of each cycle thereafter is to occur in-clinic to allow for pre-treatment assessments and to accommodate PK sampling. In subjects receiving the combination, on days when nivolumab and ipilimumab are administered, ivosidenib should be administered approximately 30 minutes before the start of the nivolumab infusion.
18. Nivolumab is to be administered over an approximately 30-minute IV infusion. Sites should make every effort to target infusion timing to be as close to 30 minutes as possible. However, given the variability of infusion pumps from site to site, a window between -5 minutes and +10 minutes is permitted (*i.e.*, infusion time is 30 minutes (-5 minutes/+10 minutes). When study treatments nivolumab and ipilimumab are to be administered on the same day, nivolumab is to be administered first. Nivolumab infusion must be promptly followed by a flush of diluent to clear the line of nivolumab before starting the ipilimumab infusion. The second infusion will always be the ipilimumab study treatment and will start after the infusion line has been flushed, filters changed, and subject has been observed to ensure that no infusion reaction has occurred.
19. Ipilimumab is to be administered over an approximately 30-minute IV infusion. Sites should make every effort to target infusion timing to be as close to 30 minutes as possible. However, given the variability of infusion pumps from site to site, a window between -5 minutes and +10 minutes is permitted (*i.e.*, infusion time is 30 minutes (-5 minutes/+10 minutes). When study treatments nivolumab and ipilimumab are to be administered on the same day, nivolumab is to be administered first. Nivolumab infusion must be promptly followed by a flush of diluent to clear the line of nivolumab before starting the ipilimumab infusion. The second infusion will always be the ipilimumab study treatment and will start after the infusion line has been flushed, filters changed, and subject has been observed to ensure that no infusion reaction has occurred. The time in between nivolumab and ipilimumab infusions is expected to be within approximately 30-minutes.
20. Treatment compliance for ivosidenib is to be assessed based on the drug diary and/or return of unused drug.
21. Tumor tissue for retrospective central laboratory confirmation of IDH1 gene mutation status and exploratory biomarker analysis at Screening is requested. Subjects will have locally documented presence of the IDH1 gene mutation for inclusion. If a subject cannot undergo a biopsy at Screening, collection of archival tumor tissue from the most recent biopsy/resection of at least 20 freshly cut, unstained FFPE slides (4-

5 µm each) plus 1 H&E slide will be submitted at a later time together with the pathology report upon sponsor's request. Tumor biopsies are to be collected at baseline, C3D1, and EOT from similar anatomical locations for exploratory biomarker analyses including PK/PD. In case of limited tissue amounts, biopsy samples will be formalin fixed and paraffin embedded. Please refer to the laboratory manual for priorities in tissue processing. If a required tumor biopsy (any time point) cannot be performed due to concerns around subject safety, a discussion with the Sponsor is required and biopsy can be omitted. Further details on screening and on-treatment biopsy collections are provided in the laboratory manual. Additional unscheduled tumor biopsy collected as standard of care, if any, will be used for the optional analysis of biomarkers (including genomic biomarkers).

22. A buccal swab for germ-line mutation analysis will be obtained at Screening.
23. Blood samples for exploratory biomarker assessments, including plasma circulating tumor DNA, will be collected at Screening and Day 1 of every cycle through Cycle 6, followed by every 6 months thereafter, and at EOT.
24. From the time of informed consent signing through the first dose of IMP, SAEs resulting from a study-related procedure and assessed as related to that procedure, as well as all fatal AEs whether or not related to research procedures, must be recorded. All AEs will be recorded from all subjects from the date of first dose through 30 days following the last dose of ivosidenib and/or nivolumab or ipilimumab, whichever occurs later. Following the 30-day Safety Follow-up period, any SAEs that occur within 100 days after last dose of immunotherapy are to be reported, or until the subject initiates another anti-cancer therapy, whichever is earlier. Only SAEs that are considered as related to either IMP by the Investigator are to be reported after the respective Safety Follow-up periods. Fatal events, related or not to the research, occurring after ICF signature and before first IMP administration, must be reported on an AE form.
25. All concomitant medications/procedures within 21 days of the first dose of IMP through 30 days (+ 5 days) after the last dose of ivosidenib and/or immunotherapy and through 100 days after the last dose of immunotherapy (whichever is later) are to be reported on the eCRF.
26. Subjects will be contacted every 12 weeks (\pm 2 weeks) after the subject experiences documented disease progression or begins subsequent anti-cancer therapy for up to 2 years after the last subject has been enrolled, or until death, lost to follow-up, withdrawal of consent from overall study participation, or Sponsor ending study, whichever occurs first.

Table (4.1.2) 2 - Pharmacokinetic and Pharmacodynamic Sampling for Subjects in the Safety Lead-in Phase: Ivosidenib in Combination with Nivolumab and Ipilimumab

Visit/Cycle:	Screening	Cycle 1 (21 Days)		Cycle 2 (21 Days)	Cycle 3 (21 Days)	Cycle 4 (21 Days Each Cycle)	Cycle 5 and Beyond (28 Days Each Cycle)
Study Day:	D-28 to D-1	D1	D15 (± 2 Days)	D1 (± 2 Days)	D1 (± 2 Days)	D1 (± 2 Days)	D1 (± 2 Days)
Blood Sample for Ivosidenib PK Pre-dose ^{1,2,3}		X	X	X	X	X	X ³
Blood Sample for PD (2-HG) Pre-dose ^{1,2,3}		X	X	X	X	X	X ³
Blood Sample for Nivolumab PK and Nivolumab ADA Pre-dose ^{1,2,4}		X		X	X	X	X ⁴
Blood Sample for Ipilimumab PK and Ipilimumab ADA Pre-dose ^{1,2,5}		X		X	X	X	
Tumor Biopsy for Ivosidenib PK Pre-dose ^{6,7}	X						
Tumor Biopsy for Ivosidenib PK Post-dose ⁶					X (± 7 days for biopsy collection)		
Tumor Biopsy for PD (2-HG) Pre-dose ^{6,7}	X						
Tumor Biopsy for PD (2-HG) Post-dose ⁶					X (± 7 days for biopsy collection)		
Blood Sample for Nivolumab and Ipilimumab PK Post-dose ⁸		X (EOI)					
Blood Sample for Ivosidenib PK Post-dose ⁸					X		
2 Hours post-dose					X		
3 Hours post-dose					X		
4 Hours post-dose					X		
6 Hours post-dose					X		

Abbreviations: 2-HG = 2-hydroxyglutarate; ADA = anti-drug antibody; D = Day; EOI = End of Infusion; PD = pharmacodynamic; PK = pharmacokinetic.

1. On the days when pre-dose samples are to be collected, subjects should be instructed to not take that day's dose of ivosidenib, nivolumab or ipilimumab dose until PK/PD samples have been collected (ivosidenib dose is to be administered in the clinic).
2. Pre-dose blood samples for ivosidenib, nivolumab, and ipilimumab PK, ADA, and 2-HG are to be collected from all subjects within 30 minutes before ivosidenib, nivolumab, and ipilimumab dosing. All pre-dose samples may be collected in one blood draw.
3. Pre-dose blood samples for ivosidenib PK and 2-HG are to be collected on C1D1, C1D15, C2D1, C3D1, C4D1, C5D1, and Day 1 of every cycle through Cycle 13, and Day 1 of every other cycle thereafter (e.g., Cycles 15, 17, etc.).
4. Pre-dose blood samples for nivolumab PK and nivolumab ADA are to be collected on C1D1, C2D1, C3D1, C4D1, and Day 1 of every 4 cycles up to 2 years (e.g., C8D1, C12D1, etc.)
5. Pre-dose blood samples for ipilimumab PK and ipilimumab ADA are to be collected on C1D1, C2D1, C3D1, and C4D1.
6. Refer to the lab manual for details on tumor biopsy collection.
7. If a subject cannot undergo a biopsy at Screening, archived fresh-frozen tumor biopsy, if available, can be used for the measurement of baseline 2-HG.
8. Post-dose blood samples to be collected within ± 10 minutes of the specified time.

Table (4.1.2) 3 - Pharmacokinetic and Pharmacodynamic Sampling for Subjects in the Expansion Phase: Ivosidenib in Combination with Nivolumab and Ipilimumab

Visit/Cycle:	Screening	Cycle 1 (21 Days)		Cycle 2 (21 Days)	Cycle 3 (21 Days)	Cycle 4 (21 Days)	Cycle 5 and beyond (28 Days Each Cycle)
Study Day:	D-28 to D-1	D1	D15 (± 2 Days)	D1 (± 3 Days)	D1 (± 2 Days)	D1 (± 2 Days)	D1 (± 2 Days)
Blood Sample for Ivosidenib PK Pre-dose ^{1,2,3}		X	X	X	X	X	X ³
Blood Sample for PD (2-HG) Pre-dose ^{1,2,3}		X	X	X	X	X	X ³
